## 2. Dosing Intensities

- (1) Actual dose intensity (mg/week) will be calculated as the total actual cumulative dose received divided by duration of treatment (weeks) for CMP-001 and Nivolumab, respectively.
- (2) Planned dose intensity (mg/week) will be calculated as the total planned cumulative dose to be received divided by the Planned Duration of Treatment (weeks) based on the protocol schedule.

Planned Duration of Treatment (weeks) = number of planned treatments \* 3 (weeks)

(3) Relative dose intensity (%) will be calculated based on the actual cumulative dose received relative to the planned cumulative dose throughout the duration of treatment as follows:

Relative dose intensity (%) = (actual dose intensity / planned dose intensity) \* 100%

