- 21. Participation in another clinical study of an investigational anticancer therapy or device within 30 days before first dose of study treatment on W1D1. NOTE: Participation in the follow-up phase (receiving no study treatment) of a prior study is allowed.
- 22. Requires prohibited treatment (ie, non-protocol specified anticancer pharmacotherapy, surgery, or radiotherapy) for treatment of malignant tumor.
- 23. Has a life expectancy of less than 3 months and/or has rapidly progressing disease (eg, tumor bleeding, uncontrolled tumor pain) in the opinion of the treating Investigator.
- 24. Received previous CMP-001 treatment.
- 25. Pregnant or breastfeeding or expecting to conceive or donate eggs within the projected duration of the study, from the time of consent until at least 150 days after last dose of study treatment for women.

Investigational product, dosage, and mode of administration:

Subjects will receive CMP-001 10 mg weekly for 7 doses (W1D1 to W7D1), after which CMP-001 will be administered every 3 weeks (Q3W) (W10D1, W13D1, etc.) until the subject meets a condition for discontinuation of study treatment. The first dose of CMP-001 may be administered subcutaneously (SC) or by IT injection at the discretion of the Investigator; all subsequent doses are planned to be administered by IT injection. The initial 7 CMP-001 weekly dose schedule must be completed before starting the Q3W CMP-001 dosing schedule.

Subjects will receive nivolumab 360 mg IV over 30 minutes at W1D1 and Q3W thereafter until the subject satisfies a condition for study treatment discontinuation. Please refer to the nivolumab Investigator's Brochure. The subjects will be first dosed with CMP-001 followed by nivolumab.

Duration of treatment:

Subjects will continue study treatment until they reach a reason for treatment or study discontinuation (Section 4.5. and Section 4.6.). Subjects may continue study treatment beyond progression based upon Investigator judgment of potential benefit. Treatment will be given for a maximum of 2 years from the start of study treatment.

If a subject achieves and maintains a confirmed CR or immune complete response (iCR) by investigator review, treatment with CMP-001 or the combination of CMP-001 and nivolumab may be discontinued at the Investigator's discretion once they meet both of the following criteria:

- Subject has been treated with both study treatments for at least 48 weeks

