3. INVESTIGATIONAL PLAN

3.1. Overall Study Design

This is a multicenter, open-label, Phase 2 clinical study of CMP-001 IT in combination with nivolumab IV in subjects with unresectable or metastatic melanoma refractory to PD-1 blockade. Eligible subjects must have confirmed disease progression during or within 12 weeks of their last dose of therapy containing a PD-1 blocking antibody for the treatment of unresectable cutaneous melanoma before enrollment. All subjects will receive CMP-001 IT and nivolumab IV according to the Schedule of Assessments (Table 1) until a reason for treatment discontinuation is reached.

Tumor tissue collection will be obtained as per instructions in the laboratory manual.

CMP-001 10 mg IT will be administered weekly for 7 doses, after which it will be administered Q3W until the subject meets a condition for discontinuation of study treatment. The first dose of CMP-001 may be administered SC or by IT injection, at the discretion of the Investigator; all subsequent doses are planned to be administered IT. The initial 7 CMP-001 doses on a weekly schedule must be completed before moving on to the Q3W CMP-001 dosing schedule.

If all injectable tumors regress, CMP-001 may be injected SC in the region of prior tumors or draining lymph node bed, at the Investigator's discretion (see Appendix G). On visits where both study treatments are administered, CMP-001 IT should be administered before nivolumab. CMP-001 should be administered until a reason for treatment discontinuation is reached. See Section 5.1.3. for treatment modifications for CMP-001.

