## II. Study Design

### A. Design Overview

This is a multicenter, open-label, exploratory Phase 2 clinical study of CMP-001 IT in combination with Nivolumab IV in subjects with unresectable or metastatic melanoma refractory to PD-1 blockade. Eligible subjects must have confirmed disease progression during or within 12 weeks of their last dose of therapy containing a PD-1 blocking antibody for the treatment of unresectable cutaneous melanoma prior to enrollment. All subjects will receive CMP-001 IT and Nivolumab IV according to the Schedule of Assessments (Protocol Table 1) until a reason for treatment discontinuation is reached.

CMP-001 10 mg IT will be administered weekly for 7 doses, after which it will be administered Q3W until the subject meets a condition for discontinuation of study treatment. The treatment will be given for a maximum of 2 years from the start of the study treatment. The first dose of CMP-001 may be administered SC or by IT injection, at the discretion of the Investigator; all subsequent doses are planned to be administered IT. The initial 7 CMP-001 doses on a weekly schedule must be completed before moving on to the Q3W CMP-001 dosing schedule.

If all injectable tumors regress, CMP-001 may be injected SC in the region of prior tumors or draining lymph node bed, at the Investigator's discretion (see Protocol Appendix F). On visits where both study treatments are administered, CMP-001 IT should be administered before Nivolumab. CMP-001 should be administered

Regeneron Pharmaceuticals Inc. / Protocol: CMP-001-010 IQVIA Biotech (Confidential) Project # RZA44091

[figure not shown]
until a reason for treatment discontinuation is reached, or for a maximum of 2 years from the start of the study treatment. See Protocol Section 5.1.3. for treatment modifications for CMP-001.

Objective responses will be assessed by BICR and Investigator assessment according to RECIST v1.1. Subjects who continue study treatment beyond PD according to RECIST v1.1 at the discretion of the Investigator will be evaluated by the Investigator according to iRECIST.

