### A. Exposure

Exposure to CMP-001 and Nivolumab will be summarized separately with descriptive statistics for the number of doses received, the duration of treatment to each drug (weeks), the planned dose intensity, the actual dose intensity, and the relative dose intensity (%).

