### 1. Duration of Treatment

Duration of Treatment (DoT) of CMP-001 and Nivolumab will be summarized in a descriptive manner, respectively. DoT will be calculated as follows:

DoT (weeks) = [min(last dose date + 21 days, discontinuation/completion date) – first dose date] / 7

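### The SAP's planned-duration formula allots 3 weeks to every CMP-001 dose although doses 1 to 7 are weekly, so on-schedule relative dose intensity reads up to 233% instead of 100%

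*SAP*

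**What the plan says.** SAP section IX.A (Exposure) has each drug summarised separately for number of doses, duration of treatment, and "the planned dose intensity, the actual dose intensity, and the relative dose intensity". Section IX.A.1 measures duration of treatment (DoT) from the first dose to the earlier of 21 days after the last dose and the discontinuation or completion date.

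Section IX.A.2 then gives three items:

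1. Actual dose intensity is cumulative dose received divided by DoT, for each drug.
2. Planned dose intensity is planned cumulative dose divided by the "Planned Duration of Treatment (weeks) based on the protocol schedule". The formula that follows is "Planned Duration of Treatment (weeks) = number of planned treatments", multiplied by 3 weeks. There is no separate formula for CMP-001.
3. Relative dose intensity (RDI) is described as "actual cumulative dose received relative to the planned cumulative dose throughout the duration of treatment", and computed as actual over planned dose intensity, times 100%.

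On the schedule, SAP section II.A states "CMP-001 10 mg IT will be administered weekly for 7 doses, after which it will be administered Q3W". Protocol section 3.1 adds: "The initial 7 CMP-001 doses on a weekly schedule must be completed before moving on to the Q3W CMP-001 dosing schedule". Protocol Table 1 numbers the CMP-001 injections 1 to 7 for W1D1 to W7D1 and 8 onward for the 3-weekly visits. Nivolumab is given at W1D1 and every 3 weeks after that.

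**The concern.** A multiplier of 3 weeks per treatment is right only for a drug given every 3 weeks. For CMP-001 it stretches the 7-dose weekly phase to a planned 21 weeks, which contradicts item (2)'s own appeal to the protocol schedule.

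Planned intensity is then too low and RDI too high. The statistic exists to show under-delivery, and Protocol section 5.1.3 handles CMP-001 toxicity by delaying the injection, with no change in dose. Under the formula as written, 100% no longer means on schedule, and a subject with delayed or missed doses can still show more than 100%. SAP section I.B says the SAP governs where it differs from the protocol, so a programmer following section IX.A.2 would produce these values.

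**Working it through.** The documents state no RDI value, so there is no figure to reproduce. The check applies the SAP formulas to a subject dosed exactly on the protocol calendar.

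**Inputs.** CMP-001 10 mg on days 0, 7, …, 42, then every 21 days (Protocol Synopsis, sections 3.1 and 5.1.2; SAP II.A). DoT from SAP IX.A.1, with the full 21 days after the last dose. Intensities from SAP IX.A.2, with each injection counted as one treatment.

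**Formulas for n doses on schedule**

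- DoT, n ≤ 7: (7(n − 1) + 21)/7 = n + 2 weeks.
- DoT, n ≥ 7: (42 + 21(n − 7) + 21)/7 = 3n − 12 weeks.
- Planned intensity as written: 10n/(3n) = 3.33 mg/week; n cancels.
- RDI as written: (10n/DoT)/(10/3) = 3n/DoT.

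| Doses (week of last dose) | DoT (weeks) | RDI as written |
|---|---|---|
| 1 (W1) | 3 | 3/3 = 100% |
| 2 (W2) | 4 | 6/4 = 150% |
| 7 (W7) | 9 | 21/9 = 233% |
| 8 (W10) | 12 | 24/12 = 200% |
| 9 (W13) | 15 | 27/15 = 180% |
| 12 (W22) | 24 | 36/24 = 150% |
| 20 (W46) | 48 | 60/48 = 125% |
| 39 (W103) | 105 | 117/105 = 111% |

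The peak is at 7 doses: actual 70/9 = 7.78 mg/week against planned 70/21 = 3.33 mg/week.

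**Nivolumab.** On schedule, DoT = 3n weeks and planned duration = 3n weeks, so RDI is 100% at every n. The multiplier is wrong for CMP-001 only.

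**Delayed or missed CMP-001 doses, as written**

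- 7 doses, 14-day delay from dose 4: DoT 11, RDI 21/11 = 191%.
- 9 doses, 14-day delay at dose 8: DoT 17, RDI 27/17 = 159%.
- 6 of the 7 weekly doses, last at W7: DoT 9, RDI 18/9 = 200%.
- 3 of the 7 weekly doses, last at W7: DoT 9, RDI 9/9 = 100%, although 3/7 = 43% of the planned dose was given.
- For n ≥ 7, RDI = 100% requires DoT = 3n, which is 12 weeks above the on-schedule 3n − 12. Delays must total 12 weeks before RDI falls to 100%.

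**If *planned treatments* meant 3-week cycles.** Count the cycles begun by the last dose, and planned doses up to the last dose; RDI is then 3 × cycles/DoT:

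- n = 1 to 6: 3/3 = 100%, 3/4 = 75%, 3/5 = 60%, 6/6 = 100%, 6/7 = 86%, 6/8 = 75%.
- n = 7 to 39: 100%.

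If planned doses are counted for every full cycle begun, on-schedule RDI is 33%, 50%, 60%, 67%, 71% and 75% at 1 to 6 doses, and 100% from dose 7.

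**Truncated DoT.** The documents give no discontinuation dates. As an illustration for 7 on-schedule doses: with discontinuation 14 days after the last dose, DoT = 8 and RDI = 21/8 = 262.5%; at 7 days, DoT = 7 and RDI = 21/7 = 300%. Planned duration is not shortened in the same way, so truncation raises RDI for either drug.

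**The case against.** The strongest defence is that *planned treatments* is undefined. Read as 3-week cycles, in line with the reference to the protocol schedule, the formula gives 100% to everyone who completes the weekly phase on time. That is true, but the SAP never says cycles, and Protocol section 5.1.2.3.1 uses treatment visit for a single CMP-001 injection visit. The cycle reading also fails for early stoppers under either way of counting planned doses. Those two counting rules are assumptions made for this check, since the SAP gives none.

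A second defence is that this is one descriptive statistic in a single-arm study of 44 subjects in which all analyses are now exploratory. Dose counts, DoT, dose modifications and dated dose listings are reported separately. This stands: it limits the consequence but does not make the reported number right.

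Third, the distortion shrinks with exposure. At 20 doses with 8 weeks of accumulated delay, RDI as written is 60/56 = 107%. This also stands: values well above 100% despite delays belong mainly to shorter exposure.

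Finally, a correction based on doses received does not equal cumulative dose over planned dose when weekly doses are skipped: 8/9 = 89% against 6/7 = 86% for 6 of 7 doses, and 5/9 = 56% against 43% for 3 of 7. This is a real difference in definition and should be stated openly. The correction follows the ratio of intensities that item (3) already displays as its formula.

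**Conclusion.** The formula is wrong as written for CMP-001. On-schedule RDI exceeds 100% from the second dose, peaks at 233% at 7 doses and is still 111% at 39. These values assume that each injection is a treatment and that DoT runs the full 21 days past the last dose; an earlier discontinuation date raises them. The 100% benchmark assumes that plan and actual cover the subject's own treatment period, as item (3) describes.

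The damage is limited to the CMP-001 planned and relative dose intensity in the exposure table. Because the underlying dosing data are reported, the correct value can be recovered. The primary response rate, the other endpoints and the analysis sets do not depend on it. It should be corrected before the exposure tables are produced.

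**What to change.** In SAP section IX.A.2:

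- Define n as the number of doses received, full or partial.
- For CMP-001, set planned duration to n + 2 weeks for n ≤ 7 and 9 + 3(n − 7) weeks for n ≥ 7, and planned intensity to 10n mg divided by that duration. Keep n × 3 weeks for nivolumab.
- For the dose intensity of both drugs, end the actual duration at last dose + 21 days without truncation, so that actual and planned durations share one end rule. The section IX.A.1 definition can stay for the DoT summary.
- Reword item (3) as actual over planned dose intensity. Doses withheld after the last dose remain visible in the dose-modification table (section IX.A.3).

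Check of the corrected rule:

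- On-schedule RDI is 100% at every dose count from 1 to 39.
- A 14-day delay from dose 4 (7 doses) gives 9/11 = 82%.
- A 14-day delay at dose 8 (9 doses) gives 15/17 = 88%.
- A seventh dose 2 days early or late, within the visit window, gives 63/61 = 103% or 63/65 = 97%.

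The cost is SAP wording and a small change to the exposure programming. No new data are needed, and no dose or schedule changes.

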### 3. Dosage Modifications

### Statistical Analysis Plan

Regeneron Pharmaceuticals Inc. / Protocol: CMP-001-010 IQVIA Biotech (Confidential) Project # RZA44091

The number of subjects with dose modifications (e.g., Drug Delayed, Drug Withheld, Drug interrupted, Dose Reduced, Drug Permanently Withdrawn) with the reasons will also be summarized by study drug.

Listings will be provided with the information from the study drug administration eCRFs for CMP-001 and Nivolumab, including date and time of each dose, route of administration, dose administered, location of each injection, and the volume injected into each tumor at each dosing visit.

### **B.** Adverse Events

Adverse events should be recorded upon first occurrence and followed until resolution. A persistent AE is continuous and does not resolve between Q3W dosing visits and should be documented only once unless the grade becomes more severe. If the grade becomes more severe, the AE must be reported again with the new grade. Any recurrent AE should be reported as new AE each time the AE occurs. Worsening of an ongoing AE (i.e., an increase to higher grade) should be recorded as a new AE. Ongoing AEs that decrease in severity/grade should not be captured as new AEs.

Immune-mediated AEs can include events with an alternate etiology that were exacerbated by the induction of autoimmunity. In the EDC system, each AE is classified as immune-mediated or not by the Investigator.

Per protocol section 8.1.1, disease progression, and associated hospitalizations and deaths, are not considered an AE or SAE in this study.

Medical occurrences that begin before start of study treatment should be recorded on the Medical History/Current Medical Conditions section of the eCRF, not the AE section.

Adverse events starting more than 100 days after the last dose of study treatment should not be recorded on the AE eCRF unless they are considered to be related to study treatment.

Serious adverse events and AEs resulting in discontinuation will be followed until one of the following occurs:

- The event resolves
- The event stabilizes
- The event returns to a Baseline value if a Baseline value is available
- The event can be attributed to agents other than the study treatment or to factors unrelated to study conduct

### Statistical Analysis Plan

Regeneron Pharmaceuticals Inc. / Protocol: CMP-001-010 IQVIA Biotech (Confidential) Project # RZA44091

• The Investigator and Medical Monitor agree that follow-up is no longer necessary

Adverse event (AE) data are available to the Sponsor from two sources: the eCRFs and the Serious Adverse Event (SAE) paper forms and corresponding SAE narratives. While reconciliation will be performed to ensure consistency between the two types of data, the production of data summaries and listings will be based on the data collected on the eCRF.

*Treatment-emergent adverse event (TEAE)* 

Pretreatment AEs are AEs that occur from the time of informed consent up to the first dose of study treatment (W1D1). A treatment-emergent adverse event (TEAE) is defined as an AE that started or worsened in severity on or after the date that study treatment was first administered (W1D1) until 100 days after the last dose of study treatment or a new cancer treatment is initiated, whichever occurs first.

Treatment-emergent adverse events will be coded using MedDRA (version 23.1 or later) and data will be summarized for the Safety Analysis Set. The number and percent of subjects reporting each TEAE will be summarized, as well as the number of TEAEs. A subject with 2 or more TEAEs within the same level of summarization (i.e., system organ class or preferred term) will be counted only once in that level using the most severe event or most related (for the relationship to study treatment tables).

AEs are graded using Common Terminology Criteria for Adverse Events (CTCAE) Version 5.0. AE summaries may include summaries for all AEs and by the maximum CTCAE grade for the item being summarized (i.e., SOC or PT). In these cases, the outputs will include a row for All Grades as well as rows for the 5 potential CTCAE grades: Grade 1 (Mild), Grade 2 (Moderate), Grade 3 (Severe), Grade 4 (Life threatening or disabling), or Grade 5 (Death).

If grade is missing for a TEAE, the event will be counted as grade 3=severe in the TEAE summary tables. If relationship is missing for a TEAE, the event will be counted as related in the TEAE summary tables.

An AE preferred term reported by a subject more than once will be represented in the most severe category or most related (for the relationship to study treatment tables).

A TEAE summary table will be generated including the following (N (%)):

- Subjects with one or more TEAEs
- Subjects with TEAEs of grade 3 or higher

## Statistical Analysis Plan

Regeneron Pharmaceuticals Inc. / Protocol: CMP-001-010 IQVIA Biotech (Confidential) Project # RZA44091

- Subjects with CMP-001 treatment-related TEAEs (includes TEAEs which are definitely, probably and possibly related and those with missing relationship)
- Subjects with Nivolumab treatment-related TEAEs (includes TEAEs which are definitely, probably and possibly related and those with missing relationship)
- Subjects with grade 3 or higher CMP-001 treatment-related TEAEs (includes TEAEs which are definitely, probably and possibly related and those with missing relationship)
- Subjects with grade 3 and higher Nivolumab treatment-related TEAEs (includes TEAEs which are definitely, probably and possibly related and those with missing relationship)
- Subjects with Serious AEs (SAEs)
- Subjects with CMP-001 treatment-related SAEs (includes TEAEs which are definitely, probably and possibly related and those with missing relationship)
- Subjects with Nivolumab treatment-related SAEs (includes TEAEs which are definitely, probably and possibly related and those with missing relationship)
- Subjects with TEAEs leading to CMP-001 treatment discontinuation
- Subjects with TEAEs leading to Nivolumab treatment discontinuation
- Subjects with immune-mediated AEs as assessed by the Investigator
- Subjects with TEAEs resulting in death

The following additional AE summaries by SOC/PT will be produced:

- All TEAEs
- Grade 3 or higher TEAEs
- TEAEs by maximum grade and maximum relationship
  - TEAEs related to any study drug (includes TEAEs which are definitely, probably and possibly related and those with missing relationship)
  - TEAEs related to CMP-001 (includes TEAEs which are definitely, probably and possibly related and those with missing relationship)
  - TEAEs related to Nivolumab (includes TEAEs which are definitely, probably and possibly related and those with missing relationship)
- TEAEs by maximum grade
- TEAEs by maximum relationship to CMP-001
- TEAEs by maximum relationship to Nivolumab

### Statistical Analysis Plan

Regeneron Pharmaceuticals Inc. / Protocol: CMP-001-010 IQVIA Biotech (Confidential) Project # RZA44091

- Grade 3 or higher TEAEs related to CMP-001 (includes TEAEs which are definitely, probably and possibly related and those with missing relationship)
- Grade 3 or higher TEAEs related to Nivolumab (includes TEAEs which are definitely, probably and possibly related and those with missing relationship)
- TEAEs of Special Interest
- TEAEs resulting in death
- All SAEs
  - SAEs related to any study drug (includes TEAEs which are definitely, probably and possibly related and those with missing relationship)
  - SAEs related to CMP-001 (includes TEAEs which are definitely, probably and possibly related and those with missing relationship)
  - o SAEs related to Nivolumab (includes TEAEs which are definitely, probably and possibly related and those with missing relationship)
- TEAEs leading to treatment discontinuation of any study drug
- TEAEs leading to CMP-001 treatment discontinuation
- TEAEs leading to Nivolumab treatment discontinuation

A hierarchical listing will display the MedDRA system organ classes represented in the data. Within each system organ class, the listing will display each unique preferred term. Within each preferred term, the listing will display each unique verbatim (recorded) term. Listed terms will be ordered alphabetically.

The following AE listings will be produced:

- All TEAEs
- Grade 3 or higher TEAEs
- TEAEs considered related to study treatment (includes TEAEs which are definitely, probably and possibly related and those with missing relationship)
- TEAEs resulting in death
- SAEs
- Related SAEs. This listing will include serious TEAEs with a drug relationship of "Possibly Related," "Probably Related", "Definitely Related." It will also include serious TEAEs with missing drug relationships.
- TEAEs leading to treatment discontinuation

Regeneron Pharmaceuticals Inc. / Protocol: CMP-001-010 IQVIA Biotech (Confidential) Project # RZA44091

